**Background:**

Post-traumatic osteoarthritis (PTOA) is a common disabling condition following intra-articular fractures (IAFs), despite best treatment efforts (1,2). Between 23% and 44% of patients develop PTOA after tibial plateau fractures (3-5) and >50% of patients after tibial pilon fractures (6-11). In one study, 30% of ankles had PTOA within 2-4 years after a pilon fracture (11). PTOA brings substantial pain, disability, lost work capacity, and decreased general health status. In the ankle, where the vast majority of OA is post-traumatic, the associated impairment is comparable to that caused by end-stage kidney disease or congestive heart failure (12,13). The societal cost of PTOA is high; ~\$12 billion/year in the United States (13) since pain and lost function frequently leads to lost work capacity. Recent findings indicate that IAFs, by virtue of both acute and chronic mechanical factors, initiate a sequence of biologic events leading to PTOA (14). Clinical trials of agents aimed at interrupting this sequence of events face barriers of limited capability to predict PTOA risk and poor early indicators of PTOA development. We have established methods to quantify PTOA risk from mechanical factors, a critical step in overcoming these barriers. There remains an urgent need for better PTOA imaging biomarkers. Diagnosis and prognosis, as well as evaluation of therapeutic efficacy, require biomarkers sufficiently sensitive to detect development and progression of disease (15). Clinical monitoring for PTOA following IAF presently involves the serial acquisition of weight-bearing radiographs to check for joint degeneration (16). However, radiographs capture an obscured 2D projection of a complex 3D structure and pathology. Our working hypothesis is that a low-dose standing CT (SCT) scanner for the foot and ankle will provide more sensitive and responsive measures of joint degeneration, without an increase in cost or time and without a significant increase in radiation (17). SCT would provide much greater diagnostic value, not only because of its 3D nature, but also because patients are imaged in a functional weight-bearing position. The SCT scanner will also simplify articular contact stress computation and could guide earlier preventive therapies.

**Specific Aims:**

Aim 1. Determine the extent to which OA findings on SCT correlate earlier and more strongly with joint symptoms than findings on plain radiographs.

Aim 2. Measure the incidence of PTOA following surgical fracture reduction in patients with tibial pilon fractures and quantify the extent to which post-reduction contact stress predicts risk and correlates with changes in 3D joint space width.

Aim 3: Identify post-injury inflammatory cytokine synovial biomarkers that correspond with worse PROMIS-29 scores.

Hypothesis: Acute IL-1b concentration in synovial fluid is associated with worse PROMIS-29 score at 12 months post-injury

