## **Procedures**

Individuals who present to hospital with an IAF of the tibial plafond and meet eligibility criteria will be consented to participate in this study. The only procedures that will be outside of their standard clinical care will be the WBCT scans obtained at 6, 12, and 18 months post-injury, and annually at 2-6 years post-injury, as well as several questionnaires that will be administered during the clinical visits. Questionnaires will be administered via RedCap, either with an iPad or a clinic computer. The scan will take place at their scheduled clinical visit at these time points. The scan itself takes about 5 minutes; this is the only research-related procedure. There is no follow-up beyond standard clinical care for this type of injury. Women who are capable of becoming pregnant will undergo a urine pregnancy test prior to having the WBCT scan.

Additionally, information on the timing and mechanism of injury, time from injury to surgery, length of hospital stay, any complications and/or subsequent ankle surgeries, as well as any clinic notes, imaging, and/or outcomes scores related to the calcaneus fracture will be collected from the electronic medical record. There is also an optional collection of synovial fluid sample at the time of surgery for subjects consented within the first 72 hours of injury.

Subjects are able to decide whether or not they wish to consent for the aspirate portion of this study and this decision does not interfere with their ability to participate in the other study procedures. The surgeon performing the ankle procedure will collect a small (between 2-10cc) aspirate of synovial fluid intraoperatively. If subjects participate in the synovial fluid collection portion of this study there will be additional WBCTs conducted at 3 weeks and 3 months post-injury during regularly scheduled follow ups. This aspirate would normally be considered

surgical discard, and poses minimal risk to the subject. Samples will be tested at the Central Laboratory at the University of Utah.

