Questionnaires that will be administered at each clinic visit include the Foot and Ankle Ability Measure, PROMIS Pain Interference, and PROMIS Physical Function. Each of these questionnaires will take approximately 10-15 minutes to complete. The total time allocated to these questionnaires will be approximately 30-45 minutes. Starting at the 6-month follow-up visit, the Rand 36 item SF Health Survey will be included in the batch of questionnaires administered. All of these questionnaires are study-specific and not standard of care.

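### Aim 3 names the 12-month PROMIS-29 score as its endpoint, but PROMIS-29 is not among the listed questionnaires, so the hypothesis cannot be tested as worded

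*Combined protocol and SAP*

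**What the plan says.** Specific Aims sets the Aim 3 objective as "Identify post-injury inflammatory cytokine synovial biomarkers that correspond with worse PROMIS-29 scores" and follows it with a labelled hypothesis: "Acute IL-1b concentration in synovial fluid is associated with worse PROMIS-29 score at 12 months post-injury". The predictor, instrument and time point are all named there.

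Procedures describes data collection. On questionnaires it says: "Questionnaires that will be administered at each clinic visit include the Foot and Ankle Ability Measure, PROMIS Pain Interference, and PROMIS Physical Function". It adds: "Starting at the 6-month follow-up visit, the Rand 36 item SF Health Survey will be included in the batch of questionnaires administered". On time it says: "Each of these questionnaires will take approximately 10-15 minutes to complete", and then "The total time allocated to these questionnaires will be approximately 30-45 minutes". A 12-month visit is planned, since the schedule has "WBCT scans obtained at 6, 12, and 18 months post-injury", done at clinic visits. Procedures also draws on existing records: "any clinic notes, imaging, and/or outcomes scores related to the calcaneus fracture will be collected from the electronic medical record".

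Statistical Methods has no paragraph for Aim 3. Its closing sentences plan descriptive summaries of the questionnaire scores and a general search for associations between those scores and several other measures, the synovial biomarkers among them. Neither IL-1b nor PROMIS-29 is mentioned.

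**The concern.** The instrument that defines the Aim 3 endpoint appears only under Specific Aims. The section that says what patients complete, and the section that says what is analysed, both omit it. Staff following Procedures would hold a 12-month visit and collect four other instruments. The analyst would then have a hypothesis with no matching variable and no instruction on which collected score to use instead.

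Two things make this worth settling early. A patient-reported score not taken at 12 months cannot be recovered later. And Aim 3 rests on a subset: synovial fluid is optional and limited to participants consented within 72 hours of injury. Those who give it also have extra scans at 3 weeks and 3 months, while the endpoint named for their biomarker question is not scheduled.

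**Working it through.** The documents give no sample size, power or effect size for Aim 3, so there is no design figure to reproduce. The check sets the sections side by side and then tests the questionnaire list against the stated time.

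**1. Endpoint against collection and analysis**

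| Element of the Aim 3 hypothesis | Specific Aims | Procedures | Statistical Methods |
|---|---|---|---|
| Predictor | Acute synovial IL-1b | Optional fluid sample at surgery; no analyte named | Synovial biomarkers in general; IL-1b not named |
| Instrument | PROMIS-29 | FAAM, PROMIS Pain Interference, PROMIS Physical Function; Rand 36 from 6 months | Questionnaire scores in general; PROMIS-29 not named |
| Time point | 12 months | 12-month visit planned | No time point for this analysis |
| Score to be tested | Not specified | n/a | Not specified |

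The time point is covered; the named instrument is not.

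**2. Is the list complete?** The questionnaire sentence says that the battery includes three instruments, which might leave room for others. The stated times allow a check.

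- Inputs from Procedures: 10-15 minutes per questionnaire; 30-45 minutes in total.
- Three instruments: 3 × 10 = 30 and 3 × 15 = 45, so 30-45 minutes. This equals the stated total.
- Four instruments at the same rate: 4 × 10 = 40 and 4 × 15 = 60, so 40-60 minutes. This exceeds it.

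The every-visit battery therefore reads as the three named instruments and no more. The total is stated before the Rand survey is introduced and does not allow for it, so the sum says less about the full 12-month battery. However, when the authors add an instrument at a later visit they name it, and they do not name PROMIS-29.

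**3. Could the score come from elsewhere?** The medical-record extraction names no instrument and no time point. It also ties the scores to a calcaneus fracture, whereas the eligible injury is an intra-articular tibial plafond fracture. It cannot be relied on to supply a 12-month PROMIS-29 score.

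**4. Do the two collected PROMIS measures stand in?** They are listed as separate questionnaires, and nothing in the document links either to a PROMIS-29 score. Even if they were accepted as substitutes, the plan does not say which of the two tests the hypothesis.

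**The case against.** The strongest reply is that this is a naming slip with little consequence. Two PROMIS measures are collected at every clinic visit, including the one at 12 months, and Statistical Methods already plans to relate questionnaire scores to the synovial biomarkers. The questionnaire sentence is not worded as exhaustive, outcome scores may also come from the record, and the repair may be a change of wording. Aims 1 and 2 do not depend on PROMIS-29.

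Much of this stands, and it limits the point. A reader might infer that Aim 3 cannot be tested at all. The documents do not support that: a closely related hypothesis on Physical Function or Pain Interference is testable at 12 months. A reader might also infer that the study's only hypothesis is lost. That is not so either. Background states a working hypothesis about standing CT, and Statistical Methods plans a test of dependent correlations for Aim 1 and a test of the contact-stress coefficient for Aim 2. Aim 3's is only the one carrying that label under Specific Aims.

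What the reply does not do is supply the missing endpoint. The time arithmetic weighs against an unlisted fourth every-visit instrument, the record extraction names no instrument, and no substitute is designated.

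**Conclusion.** The point holds as an internal contradiction. Specific Aims names the 12-month PROMIS-29 score; Procedures does not list it and Statistical Methods does not mention it. Followed as written, the plan yields no PROMIS-29 score, so the Aim 3 hypothesis cannot be tested as worded and no collected score takes its place. This assumes that the questionnaire list means what it names. The match between three instruments and 30-45 minutes supports that assumption without proving it.

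The effect is confined to Aim 3. It is tempting to put a false-positive rate on it, by supposing that the analyst picks the best of the four collected instruments with each tested at 0.05. The documents do not support such a figure. The 0.05 level is stated only for Aim 2, nothing says the choice would be made after seeing the data, and scores from the same patients at the same visit cannot be assumed independent. The open search for associations is also a separate matter, which would remain if PROMIS-29 were collected.

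**What to change.** Bring Specific Aims, Procedures and Statistical Methods into agreement before any biomarker-outcome analysis, by one of two routes.

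- **(a) Restate the endpoint.** Rewrite Aim 3 and its hypothesis on one named PROMIS score already collected at 12 months, either Physical Function or Pain Interference, with the other secondary. Nothing in the documents ranks them, so the choice is the sponsor's. The cost is a wording change and an endpoint narrowed from PROMIS-29 to one domain.
- **(b) Collect the named instrument.** Add PROMIS-29 to the 12-month battery and name the single domain or summary score to be tested. The cost is a protocol amendment and added questionnaire time, 10-15 minutes at the protocol's own rate. The documents give no enrolment status, but any participant already past 12 months would lack the score.

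On either route, Statistical Methods should name IL-1b as the predictor, the chosen score as the outcome and 12 months as the time point.

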## **Methods:**

### *Subjects*

#### Inclusion criteria:

- Age 18-70 years
- Intra-articular tibial plafond fracture
- Enrollment within 4 weeks of injury

#### Exclusion criteria:

- Pregnant or planning to become pregnant

## **Procedures**

Individuals who present to hospital with an IAF of the tibial plafond and meet eligibility criteria will be consented to participate in this study. The only procedures that will be outside of their standard clinical care will be the WBCT scans obtained at 6, 12, and 18 months post-injury, and annually at 2-6 years post-injury, as well as several questionnaires that will be administered during the clinical visits. Questionnaires will be administered via RedCap, either with an iPad or a clinic computer. The scan will take place at their scheduled clinical visit at these time points. The scan itself takes about 5 minutes; this is the only research-related procedure. There is no follow-up beyond standard clinical care for this type of injury. Women who are capable of becoming pregnant will undergo a urine pregnancy test prior to having the WBCT scan.

Additionally, information on the timing and mechanism of injury, time from injury to surgery, length of hospital stay, any complications and/or subsequent ankle surgeries, as well as any clinic notes, imaging, and/or outcomes scores related to the calcaneus fracture will be collected from the electronic medical record. There is also an optional collection of synovial fluid sample at the time of surgery for subjects consented within the first 72 hours of injury.

Subjects are able to decide whether or not they wish to consent for the aspirate portion of this study and this decision does not interfere with their ability to participate in the other study procedures. The surgeon performing the ankle procedure will collect a small (between 2-10cc) aspirate of synovial fluid intraoperatively. If subjects participate in the synovial fluid collection portion of this study there will be additional WBCTs conducted at 3 weeks and 3 months post-injury during regularly scheduled follow ups. This aspirate would normally be considered

surgical discard, and poses minimal risk to the subject. Samples will be tested at the Central Laboratory at the University of Utah.

Questionnaires that will be administered at each clinic visit include the Foot and Ankle Ability Measure, PROMIS Pain Interference, and PROMIS Physical Function. Each of these questionnaires will take approximately 10-15 minutes to complete. The total time allocated to these questionnaires will be approximately 30-45 minutes. Starting at the 6-month follow-up visit, the Rand 36 item SF Health Survey will be included in the batch of questionnaires administered. All of these questionnaires are study-specific and not standard of care.

#### Statistical Methods:

To address Aim 1, associations between continuous baseline pain and function scores and ordinal a) osteophyte and b) joint space width on pedCAT and radiographs will be assessed by calculating Spearman correlation coefficients. We will then test for the equality of dependent correlations from radiographs and pedCAT. For Aim 2, we will fit a logistic regression model with PTOA status as the dependent variable and injury severity and contact stress as independent variables. We will test null whether the coefficient for contact stress differs from zero at the 0.05 type-I error level. For power calculation, we made the following assumptions: (1) the correlation between fracture severity and contact stress is 0.5 and (2) the incidence of PTOA by 18 months at the mean value of contact stress is 20%. We will also employ descriptive statistic measures, using a statistics software program such as SAS or SPSS, to analyze subjects' validated outcomes questionnaire scores (baseline and post-operative). We will look for any significant associations between these scores and other outcomes, including joint space width and contact stress, and biomarkers present in the synovial fluid samples

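### Aim 1 is analysed with undefined baseline symptom scores although no baseline standing CT is scheduled, so symptoms at the time of imaging are not used and the claim of earlier correlation has no test

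*Combined protocol and SAP*

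**What the plan says.** Specific Aims gives Aim 1 as: "Determine the extent to which OA findings on SCT correlate earlier and more strongly with joint symptoms than findings on plain radiographs". It makes two claims, one about strength and one about timing.

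Statistical Methods assigns Aim 1 one analysis: Spearman coefficients for "associations between continuous baseline pain and function scores and ordinal a) osteophyte and b) joint space width on pedCAT and radiographs". It continues: "We will then test for the equality of dependent correlations from radiographs and pedCAT". No imaging visit is named.

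The schedule comes from other sections:

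- Inclusion criteria: "Enrollment within 4 weeks of injury".
- Procedures, all participants: "WBCT scans obtained at 6, 12, and 18 months post-injury, and annually at 2-6 years post-injury".
- Procedures, only those who agree to synovial-fluid collection: "there will be additional WBCTs conducted at 3 weeks and 3 months post-injury during regularly scheduled follow ups".
- Procedures, questionnaires: "Questionnaires that will be administered at each clinic visit include the Foot and Ankle Ability Measure, PROMIS Pain Interference, and PROMIS Physical Function".

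Baseline is not defined anywhere. The nearest indication is a later sentence in Statistical Methods that refers to "validated outcomes questionnaire scores (baseline and post-operative") scores, which sets baseline against post-operative.

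**The concern.** The symptom variable in the Aim 1 analysis does not match the aim. To learn whether CT reflects OA symptoms better than radiographs, the symptoms should be those present when the joint is imaged, or those that follow. A score from the weeks around a plafond fracture would be expected to reflect mainly the injury. Imaging months or years later shows whether the joint has degenerated.

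The timing half of the aim is also unaddressed. A single comparison of two correlations, with no visit attached, cannot show that one modality's correlation appears before the other's.

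Aim 1 carries the protocol's working hypothesis about standing CT, and each main-cohort participant is scheduled for eight research scans (6, 12 and 18 months, then years 2, 3, 4, 5 and 6). Followed literally, the analysis would not answer the question those scans are meant to inform, although the scores needed to answer it will be in the database.

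**Working it through.** **1. Aim against analysis**

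| Element of Aim 1 | What Statistical Methods provides |
|---|---|
| Symptoms | Baseline pain and function scores only |
| Stronger correlation | Equality test for two dependent correlations: a suitable form, but applied to baseline scores |
| Earlier correlation | Nothing: no visit, no comparison by visit, no longitudinal model |

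**2. Gap between score and scan.** Assume baseline is at enrollment, so at most 4 weeks (about 1 month) after injury.

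- Main cohort, first scan: 6 months minus 0 to 1 month = about 5 to 6 months.
- Main cohort, last scan: 6 years minus 0 to 1 month = just under 6 to 6 years.
- Optional subset: the scans at 3 weeks and 3 months can fall close to baseline. The remaining eight scans have the same gaps as the main cohort.

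**3. Same-visit data.** Scans take place at clinic visits, and the Foot and Ankle Ability Measure and both PROMIS scores are collected at each clinic visit. Same-visit pairs will therefore exist, but the Aim 1 sentence does not use them.

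**4. Illustration of the effect on power.** There is no figure in the plan to reproduce. The power assumptions in Statistical Methods concern Aim 2, and no sample size or expected correlation is given for Aim 1. Every input below is an assumption:

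- same-visit correlation with symptoms: a = 0.45 for CT and b = 0.25 for radiographs;
- correlation c between the CT and radiograph findings: 0.4, 0.6 or 0.8;
- n = 100, two-sided alpha 0.05 (the plan states 0.05 for Aim 2 only, and does not give sidedness);
- the acute score correlates k with the later score and relates to later imaging only through it, so a and b become ka and kb.

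Large-sample formulas for two correlations that share one variable:

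- cov = c(1 − a² − b²) − ½ab(1 − a² − b² − c²)
- SE² = [(1 − a²)² + (1 − b²)² − 2cov] / n
- z = (a − b)/SE; power = Φ(z − 1.96) + Φ(−z − 1.96)

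Worked case, k = 1 and c = 0.6: a² = 0.2025, b² = 0.0625, and 1 − a² − b² = 0.735.

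- cov = 0.6 × 0.735 − 0.05625 × (0.735 − 0.36) = 0.4410 − 0.0211 = 0.4199
- SE² = (0.6360 + 0.8789 − 0.8398)/100 = 0.00675, so SE = 0.082
- z = 0.20/0.082 = 2.43, and power is 68%

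Repeating this over c and k at n = 100:

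| Score used | Difference in correlation | c = 0.4 | c = 0.6 | c = 0.8 |
|---|---|---|---|---|
| Same visit (k = 1) | 0.20 | 52% | 68% | 92% |
| Acute, k = 0.5 | 0.10 | 15% | 21% | 36% |
| Acute, k = 0.2 | 0.04 | 7% | 7% | 10% |

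The formulas are for Pearson correlations. The plan uses Spearman coefficients on ordinal grades with ties, so the levels are approximate.

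**The case against.** **Baseline may be loose wording.** It is undefined and no date is given for the first questionnaire, so a reader who infers that the scores are certainly acute-fracture scores goes beyond the text. This stands as a caveat. The enrollment window and the contrast with post-operative scores favour the acute reading but do not prove it. If the first imaging visit was meant, the text needs to say so, and timing would still be untested.

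**Some early scans exist.** It is tempting to say that nobody has a standing CT before 6 months. That is true of the main cohort only. The subset's 3-week scan lies inside the 4-week enrollment window and may be close to baseline. However, it is a scheduled follow-up in an optional subset, and the plan does not limit Aim 1 to that subset.

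**The loss of power is conditional.** Shrinking both correlations by k is valid only if the acute score relates to later imaging solely through later symptoms. The Background says that intra-articular fractures start events leading to PTOA through acute and chronic mechanical factors, and the Aim 2 model includes injury severity. Severity could therefore drive both early pain and later imaging, and the shrinkage need not equal k. This stands, so the table is an illustration and not an estimate.

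**The closing sentence of Statistical Methods may cover follow-up scores.** It promises a search for associations between questionnaire scores and outcomes including joint space width. It mentions neither osteophytes nor a CT-versus-radiograph contrast, and gives no visits. It does not supply the missing analysis.

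**The problem can be repaired before analysis.** That is correct, and it is a reason to make the change, not to leave the text as it is.

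**Conclusion.** The point holds. The analysis assigned to Aim 1 uses undefined baseline scores, no standing CT is scheduled at baseline, and no analysis addresses timing. These three facts come from the text and need no assumption. If baseline is at enrollment, most scans would be paired with a score about 5 months to 6 years older.

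The size of the statistical loss is not known. Under the assumptions shown (n = 100, correlations 0.45 and 0.25), power falls from 52%–92% with same-visit scores to 15%–36% at k = 0.5 and 7%–10% at k = 0.2.

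Two stronger conclusions that a reader might draw are not supported. One is that any positive result would concern acute injury and not OA. A correlation with imaging made months later could reflect both, for example through injury severity. The other is that a null result would necessarily be taken to mean that CT is no better than radiographs. That is a risk of misreading, not something the plan says.

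**What to change.** In the Aim 1 sentence of Statistical Methods:

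1. Replace the baseline scores with the Foot and Ankle Ability Measure, PROMIS Pain Interference and PROMIS Physical Function scores from the same visit as the image. If baseline is kept anywhere, define it.
2. Run the planned comparison of dependent correlations at each standing-CT visit for which a clinical radiograph from that visit is available.
3. State how earlier correlation is judged. One option is to report the CT-minus-radiograph difference in correlation by visit. Another is to relate 6- and 12-month findings on each modality to later symptoms. Either is a fair reading of the aim, but one should be chosen in advance.

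No new scans or questionnaires are needed. The cost is a change of wording, a little more analysis, and several visit-level comparisons in place of one. It also relies on clinical radiographs: Procedures sets no research radiograph schedule, so matched films may not exist at every visit, and the number of matched pairs should be reported for each visit.

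### Aim 1 compares standing CT with radiographs on ordinal grades of joint space width; measured width on both modalities would usually give the test more power at little cost

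*Combined protocol and SAP*

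**What the plan says.** Specific Aims states Aim 1 as: "Determine the extent to which OA findings on SCT correlate earlier and more strongly with joint symptoms than findings on plain radiographs". The Statistical Methods section carries it out by assessing "associations between continuous baseline pain and function scores" against imaging findings, described as "ordinal a) osteophyte and b) joint space width on pedCAT and radiographs will be assessed by calculating Spearman correlation coefficients". It continues: "We will then test for the equality of dependent correlations from radiographs and pedCAT".

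The word ordinal stands before the a)/b) list, so on the natural reading it covers both osteophytes and width, on both modalities. The clinical scores are the only variables called continuous. The section gives no number of grades, cut-points or grading rule. Nor does it say whether the grade rates absolute width or narrowing.

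Aim 2 asks how far contact stress "correlates with changes in 3D joint space width", so a quantitative CT width is needed in any case. The Background's working hypothesis is that standing CT "will provide more sensitive and responsive measures of joint degeneration", given that "radiographs capture an obscured 2D projection of a complex 3D structure and pathology".

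The last sentence of Statistical Methods plans associations of questionnaire scores with joint space width. It names no scale and no between-modality comparison, so it does not supply a measured-width version of the Aim 1 test.

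**The concern.** Cutting a length into a few grades produces tied ranks and drops differences within a grade. A Spearman coefficient on the grades is then usually smaller than one on the measured width. When both modalities are graded, both correlations shrink, the gap between them shrinks, and the test of equality has less power to detect a true difference.

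That comparison is the substance of Aim 1, so a real CT advantage on width is more likely to be missed than it need be. Spearman's coefficient accepts measured width unchanged, so the choice of coefficient gives no reason to grade it.

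**Working it through.** **Inputs.** From the plan: ordinal width on both modalities, continuous scores, Spearman correlations, and a test of equal dependent correlations. The plan has no Aim 1 power figure to reproduce. Its 0.05 level is stated for Aim 2 only, and its power assumptions also concern Aim 2.

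Assumed: two-sided 0.05; the Meng z test (the plan names no statistic); normal latent values with correlations of 0.5 (CT–symptom), 0.3 (radiograph–symptom) and 0.6 (CT–radiograph); N = 100 as the reference case.

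**Step 1: measured width, by formula.** For normal data, Spearman = (6/π)·arcsin(r/2). So 0.5, 0.3 and 0.6 become 0.483, 0.288 and 0.582.

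The test statistic is z = (atanh r₁ − atanh r₂)·√[(N − 3) / (2(1 − rₓ)h)], with h = (1 − f·m)/(1 − m), f = (1 − rₓ)/(2(1 − m)) and m = (r₁² + r₂²)/2.

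- m = (0.233 + 0.083)/2 = 0.158; f = 0.418/1.684 = 0.248; h = 0.961/0.842 = 1.141
- Difference on the Fisher scale = 0.2305
- z = 0.2305 × √(97/0.954) = 2.32
- Power ≈ Φ(2.32 − 1.96) = 64%

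**Step 2: why grading lowers it.** With grades split 60/20/15/5, simulation gives Spearman values of 0.42 and 0.25. The Fisher-scale difference falls to 0.192. With rₓ held at 0.582, z = 1.97 and power is about 50%. Grading also lowers the CT–radiograph correlation. At an illustrative rₓ of 0.50, z = 1.81 and power is about 44%. The simulated figure is 42%.

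**Step 3: simulation over grading schemes** (N = 100, same correlations). The first five rows use 3,000 to 5,000 replicates, so the standard error of a power near 64% is at most √(0.64 × 0.36/3,000) = 0.9 points. The last row uses 1,500.

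| Grades on both modalities | Graded Spearman, CT / radiograph | Power, graded | Power, measured | Loss (points) |
|---|---|---|---|---|
| 5, even | 0.47 / 0.28 | 58.7% | 64.3% | 5.6 |
| 4, even | 0.45 / 0.27 | 53.3% | 63.1% | 9.8 |
| 3, even | 0.44 / 0.26 | 48.7% | 64.0% | 15.3 |
| 4, split 60/20/15/5 | 0.42 / 0.25 | 42.0% | 64.5% | 22.5 |
| 3, split 70/20/10 | 0.39 / 0.23 | 33.6% | 65.7% | 32.1 |
| 4, split 50/30/15/5 | 0.43 / 0.26 | 45% | 62% | 17 |

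For the first five schemes and the same correlations, power falls from about 35–37% to 19–32% at N = 50, and from about 91–93% to 62–87% at N = 200. Adding correlations of 0.4/0.25 and a between-modality value of 0.7 gives losses from about 2 to 36 points. Grading lost power in every one of these scenarios.

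**Step 4: a case with no loss.** If symptoms rise only once narrowing passes a threshold, power with the 50/30/15/5 split is 26.2% graded against 26.3% measured. At a higher threshold it is 10.9% against 10.2%. Even grades still lose about 1 to 5 points.

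**Step 5: false positives.** With equal true correlations (0.4/0.4), matched scales reject 4.5–5.9% of the time, whether both are graded or both measured. Measured CT against graded radiographs rejects about 5–21%, because only one correlation has been attenuated.

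**The case against.** **Matched grades are a legitimate design.** This stands. They put both modalities on one scale and hold the false-positive rate near 5%. The issue is efficiency, not validity. Aim 1 asks about extent and sets no power target.

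**The effect is not specific to CT.** A reader might infer that grading throws away the resolution advantage CT is meant to bring, so that Aim 1 could not show a CT benefit. The documents do not support this. In the simulations both modalities are cut alike and both correlations shrink by the same proportion (50/30/15/5 split: 0.431/0.478 = 0.90 for CT, 0.257/0.285 = 0.90 for radiographs). The Background credits CT with 3D and weight-bearing views. Either can change which grade is assigned, and that benefit survives grading. Osteophytes also remain as a second comparison.

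**The size is not fixed.** This stands. N, number of grades, their distribution and the correlations are all absent from the plan, and Step 4 shows the loss can vanish.

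**Width in mm carries normal anatomical variation that a narrowing grade might screen out.** If that variation is independent between the two images, mm can do worse: 18% power against 32–38% for grades when its SD equals that of disease. But both images show the same ankle. With the variation shared, mm gives 56–58% against 35–54% for grades. The objection largely falls.

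**Measuring radiographs in mm takes work.** This stands in part. The plan describes no scaling or reading procedure for them, and 3D width and projected width are different quantities even in the same unit.

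**Timing.** Statistical Methods refers to baseline scores, while Procedures starts the scans at 6 months for most participants. That pairing needs settling separately and does not bear on the choice of scale.

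**Conclusion.** The point holds as a cheap improvement. Aim 1 grades a length that the study already has to measure on CT, and no measured-width comparison of the modalities is planned elsewhere.

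Under the reference assumptions the avoidable loss is about 5 points of power with five even grades and about 20 points with skewed four-grade scales. It can be near zero under a threshold relation between narrowing and symptoms. None of the assumed correlations, sample sizes or grade splits comes from the documents, so these figures show direction and a plausible range, not this study's actual loss.

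Two stronger readings should not be drawn. The planned test is not invalid, since matched grades keep its error rate. A null result would not by itself be produced by grading, because the plan gives too little to say how much power the test has on either scale.

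**What to change.** In the Aim 1 part of Statistical Methods:

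- Keep ordinal grades for osteophytes.
- Use measured joint space width in mm on both modalities (3D width from CT, measured width from the radiograph) in the Spearman correlations and the dependent-correlation test.
- Report the matched graded comparison of width as a sensitivity analysis, with the number of grades and the grading rule stated.
- Do not set measured CT width against graded radiographs; under equal true correlations that pairing rejected up to about 21% of the time.

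The text change is small, and the CT width is already required for Aim 2. The real cost is reading width in mm on radiographs already collected, with a short rule for image scaling. It needs no further patients, visits or scans.
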